1.3. Schedule of Assessments

	Screening	Run-in	Double-blind Treatment					Safety Follow-up	Notes
	Visit 1	Visit 2	Visit 3	Visit 4	Visit 5	Visit 6	Visit 7	Telephone Call	
Day/Week	Day -42 to -15	Day -14	Baseline Day 1	Week 2 (Day 15)	Week 4 (Day 29)	Week 8 (Day 57)	Week 12 or Early WD (Day 85)	Week 14 or 14 days after last dose (at the latest)	
Visit Window		± 4 days		± 4 days	± 4 days	± 4 days	± 4 days	-7 days	Safety Follow-up call will occur 7 to 14 days after the last dose of study drug (includes window of -7 days) ^a
Informed consent	X								
Subject entry into IWRS and subject registry	X								
Inclusion and exclusion criteria review	X	X	X						Recheck clinical status before Run-in and randomization
Demographics	X								
Medical history and surgical history	X								Includes current use of illicit drugs, alcohol and caffeine
IBS history	X								Including previous treatments and diets
AE/SAE review	X	X	X	X	X	X	X	X	From informed consent to Safety Follow-up call
Concomitant medication review	X	X	X	X	X	X	X	X	

	Screening	Run-in	Double-blind Treatment					Safety Follow-up	Notes
	Visit 1	Visit 2	Visit 3	Visit 4	Visit 5	Visit 6	Visit 7	Telephone Call	
Day/Week	Day -42 to -15	Day -14	Baseline Day 1	Week 2 (Day 15)	Week 4 (Day 29)	Week 8 (Day 57)	Week 12 or Early WD (Day 85)	Week 14 or 14 days after last dose (at the latest)	
Visit Window		± 4 days		± 4 days	± 4 days	± 4 days	± 4 days	-7 days	Safety Follow-up call will occur 7 to 14 days after the last dose of study drug (includes window of -7 days) ^a
Vital signs	X	X	X	X	X	X	X		Body temperature, blood pressure (avg of 3 results) and pulse after sitting for 5 min and before blood draw: Visits 1 to 7 Weight: Visits 1, 3, and 7 Height: Visit 1
Brief physical examination	X		X				X		Heart, lungs, abdomen, external genitalia, perianal area, and others as needed
Urine β-hCG pregnancy test	X		X				X		Women of child-bearing potential only; serum test required if urine test positive
Urine drug screen	X	X ^c							Refer to exclusion criterion #29 and Section 6.5 for additional details on possible repeat testing at Visit 2 in the event of an initially positive result at Visit 1.

	Screening	Run-in	Double-blind Treatment					Safety Follow-up	Notes
	Visit 1	Visit 2	Visit 3	Visit 4	Visit 5	Visit 6	Visit 7	Telephone Call	
Day/Week	Day -42 to -15	Day -14	Baseline Day 1	Week 2 (Day 15)	Week 4 (Day 29)	Week 8 (Day 57)	Week 12 or Early WD (Day 85)	Week 14 or 14 days after last dose (at the latest)	

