4.4. End of Study Definition

The end of the study is defined as the date that the last subject completes both the Week 12 Visit and Week 14 Safety Follow-up Telephone Call Visit, discontinues from the study, or is lost to follow-up.

A subject is considered to have completed the study if she completes 12 weeks of double-blind treatment at the Week 12 Visit.

5. Study Population

The study is being conducted in women with IBS-D or IBS-M, which is representative of the subject population to which the results will be generalized. Specific inclusion and exclusion criteria are specified below. Prospective approval of protocol deviations to recruitment and enrollment criteria, also known as protocol waivers or exemptions, is not permitted. Subjects may be rescreened **once** to meet inclusion criteria (see [Section 5.4](#)).

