8.2.1. Symptom Diaries

Subjects will complete 2 diaries daily, a Bowel Movement Diary and a Pain Diary. The Bowel Movement Diary will be event-driven (ie, subjects will record events as they occur) and will capture bowel movement frequency and form, bowel urgency, and recurrent bowel movements. The Pain Diary will prompt subjects each evening to answer a question regarding worst abdominal pain for the past 24 hours using the 0- to 10-point NRS to rate pain and to capture use of rescue medications.

Subjects will receive the diaries and be trained on their use at the start of the Run-in Period (Visit 2). At subsequent visits, subjects will be re-instructed or retrained as needed. Subjects

must be able to complete the diaries to be eligible for the study. Further details on training and the use of the diaries are provided in a separate manual.

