10.7.3. Baseline, Visit 3 (Day 1)

- Assess inclusion/exclusion criteria
- Review concomitant medications
- Administer questionnaires (GIS, WPAI, IBS-QoL, and additional abdominal pain questions)
- Record blood pressure (average of 3 results; record each reading in the source document), body temperature, pulse, and weight
- Perform brief physical examination (heart, lungs, abdomen, external genitalia, perianal area, and any other areas as needed)
- Perform urine pregnancy test; if positive, perform serum test (subject may not begin double-blind treatment if serum pregnancy test is positive)
- Perform laboratory assessments, including urine dipstick
- Obtain subject randomization assignment
- Dispense double-blind study drug
- Administer witnessed dose of study drug
- Review AEs/SAEs

10.7.4. Double-blind Treatment Period Week 2 (\pm 4 days), Visit 4

- Administer questionnaires (GIS and additional abdominal pain questions)
- Review AEs/SAEs
- Review concomitant medications, including use of rescue medication from diary
- Record blood pressure (average of 3 results; record each reading in the source document), body temperature, and pulse
- Perform laboratory assessments, including urine dipstick
- Review remaining double-blind study drug from Baseline (Visit 3) for compliance and return to subject

10.7.5. Double-blind Treatment Period Week 4 (\pm 4 days), Visit 5

- Administer questionnaire (GIS and additional abdominal pain questions)
- Review AEs/SAEs
- Review concomitant medications, including use of rescue medication from diary
- Record blood pressure (average of 3 results; record each reading in the source document), body temperature, and pulse
- Perform laboratory assessments, including urine dipstick
- Dispense double-blind study drug

10.7.6. Double-blind Treatment Period Week 8 (\pm 4 days), Visit 6

- Administer questionnaires (GIS, WPAI, and IBS-QoL, and additional abdominal pain questions)
- Review AEs/SAEs
- Review concomitant medications, including use of rescue medication from diary
- Record blood pressure (average of 3 results; record each reading in the source document), body temperature, and pulse
- Perform laboratory assessments, including urine dipstick
- Dispense double-blind study drug

10.7.7. Double-blind Treatment Period Week 12 (\pm 4 days [Visit 7]), or Early Withdrawal

- Administer questionnaires (GIS, WPAI, IBS-QoL, and additional abdominal pain questions)
- Collect subject diary
- Review AEs/SAEs

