4.2.4.2. Analysis Visiting Window

Analysis windows will be used for eDiary, safety (vitals and labs) as well as quality of life endpoints.

All measurements including the ones from the unscheduled visits that fall within the “Visit Window” will be used in the windowing algorithm to determine the analysis visit. Relative study day will be derived based on [Section 4.3.3](#). Note that the date of the first double-blind dose is Day 1 and the day before the date of the double-blind first dose is Day -1. Thus, there is no Day 0.

For the safety assessments and quality of life endpoints, if there are multiple values for in one window, the visit closest to the nominal day will be selected for assessing endpoints at a particular visit and for by-visit displays. If the visits are equally distant from the nominal day, then the earlier visit will be selected. All values will be stored in analysis datasets.

Check that all records slotted to a post-treatment visit are greater or equal to 15 days after the last dose date. Any post-treatment visit occurring less than 15 days after the last dose date should be re-slotted to an on-treatment visit using the corresponding relative day windows constructed for that parameter.

Table 1. For eDiary, the following analysis visit window slotting will be used to determine weekly assessments:

Analysis window label	Visit Window
Screening	NA
Run-in	NA
Baseline	[-7, -1]

Analysis window label	Visit Window
Week 1	[1, 7]
Week 2	[8, 14]
Week 3	[15, 21]
Week 4	[22, 28]
Week 5	[29, 35]
Week 6	[36, 42]
Week 7	[43, 49]
Week 8	[50, 56]
Week 9	[57, 63]
Week 10	[64, 70]
Week 11	[71, 77]
Week 12	[78, 84]
Follow-Up for Early Withdrawals	>Last dose date + 14
Follow-Up for Completers	>Last dose date + 14

Note: Only calculate the upper bound of last dose date + 14 if the relative study day of the last dose date is ≥ 71 days

Table 2: Analysis Visit Window Slotting for Safety Laboratory and Vitals

Analysis window label	Nominal visit	Nominal day	Visit Window
Screening	Visit 1	NA	NA
Run-in	Visit 2	NA	NA
Baseline ¹	Visit 3	1	NA
Week 2	Visit 4	15	[2, 22]
Week 4	Visit 5	29	[23, 42]
Week 8	Visit 6	57	[43, 70]
Week 12	Visit 7	85	[71, last dose date + 14,]
Follow-Up for Early Withdrawals	NA	NA	>Last dose date + 14
Follow-Up for Completers	NA	NA	>Last dose date + 14

¹ See [section 4.3.4](#) for definition of baseline

Note: Only calculate the upper bound of last dose date + 14 if the relative study day of the last dose date is ≥ 71 days

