4.3.1.1. API Weekly Responder

To derive API Weekly Responder during various week intervals, the initial two steps should be followed to derive (1) Weekly average worst abdominal pain (WAP) score; (2) Weekly Responder status by week

Step 1:

- Weekly average is defined as the sum of WAP scores on the NRS (0-10) in the 7 days immediately prior to baseline visit (Day 1) or each of post-baseline Weeks (Week 1-Week 12), divided by the number of days with non-missing pain diary entries during the 7 days. Weekly average will be set missing if there are more than 2 missed diary days over the past 7 days.
- API Weekly Responder with $\geq 30\%$ improvement at each week (i.e., Week 1, Week 2, Week 3, ..., Week 12) is defined as a subject who experiences a decrease in the weekly average of WAP score of at least 30% compared with the baseline weekly average. To qualify as a responder for the specific week, a subject must have at least 5 days of non-missing pain diary entries during the week (i.e., ≥ 5 of 7 days). A Subject will be assigned as non-responder for the specific week if the weekly average is missing.

Similarly, the API Weekly Responder will be further derived based on more stringent measures of weekly reduction as below:

- API Weekly Responder with $\geq 40\%$ improvement at each week (i.e., Week 1, Week 2, Week 3, ..., Week 12) is defined as a subject who experiences a decrease in the weekly

average of WAP score of at least 40% compared with the baseline weekly average. To qualify as a responder for the specific week, a subject must have at least of 5 days of non-missing pain diary entries during the week (i.e., ≥ 5 of 7 days).

- API Weekly Responder with $\geq 50\%$ improvement at each week (i.e., Week 1, Week 2, Week 3, ..., Week 12) is defined as a subject who experiences a decrease in the weekly average of WAP score of at least 50% compared with the baseline weekly average. To qualify as a responder for the specific week, a subject must have at least of 5 days of non-missing pain diary entries during the week (i.e., ≥ 5 of 7 days).

Step 2:

Then API Weekly Responder will be derived during different treatment intervals using primary criteria as an example below:

API Weekly responder with $\geq 30\%$ improvement over 12 weeks (i.e., from randomization through to Week 12) - primary efficacy endpoint

- To qualify as an overall API Weekly Responder from randomization through to Week 12 (Weeks 1-12), a subject must satisfy the following criteria:

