 - Must meet the API Weekly Response criteria $\geq 30\%$ improvement on $\geq 50\%$ of weeks, i.e., success on 6 or more weeks during the past 12 weeks
 - Must have had ≥ 60 diary days over the past 12 weeks

API Weekly responder from randomization through to Week 2 (Weeks 1-2)

- To qualify as an API Weekly Responder from randomization through to Week 2, a subject must satisfy the following criteria:
 - Must meet the API Weekly Response criteria on more than 50% of weeks, i.e., success on 1 or 2 weeks during past 2 weeks
 - Must have had ≥ 10 diary days over the past 2 weeks

API Weekly Responder from randomization through to Week 4 (Weeks 1-4)

- To qualify as an API Weekly Responder over 4-week interval, a subject must satisfy the following criteria:
 - Must meet the API Weekly Response criteria on more than 50% of weeks, i.e., success on 2 or more weeks during past 4 weeks
 - Must have had ≥ 20 diary days over the past 4 weeks

API Weekly Responder from randomization through to Week 8 (Weeks 1-8)

- To qualify as an API Weekly Responder over 8-week interval, a subject must satisfy the following criteria:
 - Must meet the API Weekly Response criteria on more than 50% of weeks, i.e., success on 4 or more weeks during past 8 weeks
 - Must have had ≥ 40 diary days over the past 8 weeks

The secondary efficacy endpoints of Weekly API Responder with either $\geq 40\%$ or $\geq 50\%$ improvement will be classified using the same rules above.

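### A permitted early Visit 7 (Day 81, sometimes Day 82) leaves fewer than 5 entries in the fixed Week 12 diary window, so recorded pain data drop out of the Week 12 change scores

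*SAP*

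**What the plan says.** - **SAP 4.2.4.2:** "For eDiary, the following analysis visit window slotting will be used to determine weekly assessments". Week 12 is Days 78-84, both there and in Table 5. Day 1 is the first double-blind dose, and there is no Day 0.
- **Protocol 1.3 and 10.7.7:** Visit 7 is Day 85 ± 4 days, so Days 81-89 are all permitted. The visit's task list includes "Collect subject diary".
- **Protocol 8.2.1:** "The Pain Diary will prompt subjects each evening to answer a question regarding worst abdominal pain for the past 24 hours".
- **SAP 4.3.1.1, Step 1:** "Weekly average will be set missing if there are more than 2 missed diary days over the past 7 days", and "A Subject will be assigned as non-responder for the specific week if the weekly average is missing".
- **SAP 4.3.1.3:** the change in weekly worst pain uses that same average. Pain-free days carry the same limit on missed days. Both are derived at Weeks 2, 4, 8 and 12 only.
- **SAP 4.3.1.1, Step 2:** the 12-week responder needs "success on 6 or more weeks during the past 12 weeks" and at least 60 diary days.
- **Protocol 9.4.2:** by-visit diary summaries, weekly response included, use only the 7 days before the woman's clinic visit. The visible part of SAP Section 9 does not list the fixed windows as a departure from this.

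**The concern.** The fixed window assumes that the diary runs through Day 84. It stops earlier for a woman whose last visit falls early within the allowed range. Days on which she could no longer make an entry are then treated as days she missed, and the entries she did make that week are discarded. Only Week 12 is exposed, because the diary continues after Visits 4, 5 and 6.

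The outputs at stake are:
- the Week 12 change in weekly worst pain (Tables 14.2.3.1-14.2.3.3, topline);
- the Week 12 change in pain-free days (Tables 14.2.4.1-14.2.4.3, end of study only);
- the Week 12 point of the weekly responder plots (Figures 14.2.1.2-14.2.1.4, end of study only).

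The SAP and protocol 9.4.2 also give different Week 12 days for any Visit 7 that is not on Day 85.

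**Working it through.** **1. Reproduce the window.** The 7 days before nominal Day 85 are 85 − 7 to 85 − 1, which is Days 78-84, as in the SAP. The same holds for Weeks 2, 4 and 8: nominal Days 15, 29 and 57 give 8-14, 22-28 and 50-56.

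**2. Count possible entries in Days 78-84 for a Visit 7 on day V.** If the diary is returned before that evening's entry the count is V − 78. If that evening's entry is also made it is V − 77. Both are capped at 7.

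| Visit 7 | Returned before evening entry | Evening entry also made | Week 12 average |
|---|---|---|---|
| Day 81 | 3 | 4 | missing either way |
| Day 82 | 4 | 5 | missing only if returned before |
| Day 83 | 5 | 6 | evaluable |
| Day 84 | 6 | 7 | evaluable |
| Days 85-89 | 7 | 7 | evaluable |

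**3. Apply protocol 9.4.2 instead.** Days V − 7 to V − 1 give 7 of 7 entries for every permitted V: Days 74-80 for V = 81 and Days 75-81 for V = 82. These overlap Week 11 (Days 71-77) by 4 and 3 days, and do not touch Weeks 2, 4 or 8.

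**4. Share affected, f.** The documents give no visit-day distribution. Assume visits centred on Day 85, normal and limited to Days 81-89, with 45 evaluable IBS-D women per arm (protocol 9.2). A uniform spread is an extreme bound.

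| Assumed spread | f, Day 81 only | Women of 45 | f, all Day 81-82 visits | Women of 45 |
|---|---|---|---|---|
| SD 1.5 | 0.85% | 0.38 | 4.66% | 2.10 |
| SD 2 | 2.85% | 1.28 | 9.58% | 4.31 |
| SD 2.5 | 4.83% | 2.17 | 13.2% | 5.95 |
| Uniform | 11.1% | 5.0 | 22.2% | 10.0 |

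**5. Change scores.** With random loss, the Week 12 standard error rises by about √(1 + (1 − R²) f/(1 − f)) − 1, where R² is the assumed share of Week 12 variance explained by the other weeks (0.36-0.64). For f = 4.83% and R² = 0.36 this is √(1 + 0.64 × 0.0483/0.9517) − 1 = 1.6%. Over SD 1.5-2.5 the range is 0.15-1.6% for Day 81 only and 0.9-4.8% for Days 81-82. The uniform bounds are 3.9% and 8.8%.

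**6. Responder plots.** Missing counts as non-response, so each arm's Week 12 rate falls by f × the weekly response rate (assumed 35-50%). That is 0.3-2.4 points for Day 81 only (uniform up to 5.6) and 1.6-6.6 points for Days 81-82 (uniform up to 11.1). A 20-point gap (51% against 31%, protocol 9.2) narrows by 20 × f: 0.2-1.0 points and 0.9-2.6 points (uniform 2.2 and 4.4).

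**7. 12-week responder endpoints.** An affected woman still has at least 80 diary days against the 60 required. Her status changes only if she has exactly 5 successes in Weeks 1-11 and would have succeeded in Week 12. Under a beta-binomial (mean 35-50%, within-woman correlation 0.3-0.7) that is 1.25-4.17% of affected women. Multiplied by f this gives 0.01-0.20 points (Day 81 only) and 0.06-0.55 points (Days 81-82). The uniform bound is 0.93 points, or 0.0093 × 45 = 0.42 women per arm. For the 40% and 50% thresholds (assumed weekly response 15-30%) the bound is 0.71 points, or 0.32 women.

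**The case against.** The case for leaving the SAP alone is fair in several respects.

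- **The fixed grid is legitimate.** Protocol Section 9 calls itself a summary and leaves details to the SAP. A rule of 6 weeks out of 12 needs weeks that do not overlap. This stands, and is why the grid should stay for the 12-week endpoints. It also stands for the weekly plots: re-anchoring them could show a woman as a Week 12 responder while the 12-week endpoint counts that week as a failure.
- **Frequency is unknown.** This also stands. Every percentage above is conditional on assumptions. The upper case supposes that every Day 82 diary is returned before the evening entry, and the uniform spread has no support in the documents.
- **No decision turns on it.** The affected outputs are neither primary nor secondary, there is no formal hypothesis, and the mixed model is the SAP's chosen treatment of missing change scores. This limits the importance but does not justify discarding recorded data.
- **Completion status is inferred.** Protocol 4.4 says "A subject is considered to have completed the study if she completes 12 weeks of double-blind treatment at the Week 12 Visit". It does not say in terms that a Day 81 visit qualifies; that follows only from the visit window. The rule should therefore depend on the visit date, not on a completer label.
- **Some text is not visible.** Several SAP derivations and part of Section 9 are redacted, and diary details are in a separate manual. The absence of a reconciliation can be asserted only for the visible text.

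A reader might infer that the primary result is distorted or that one arm is favoured. The documents do not support either. Step 7 bounds the primary effect at under half a woman per arm, and nothing links visit timing to treatment. GIS is also untouched: it is completed at the visit, and its Week 12 window opens on Day 71.

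**Conclusion.** The gap is real and follows from the day count alone, given that recording ends when the diary is collected. A permitted Visit 7 on Day 81, or on Day 82 with the diary returned before that evening's entry, makes a fully compliant woman's Week 12 weekly average missing.

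The effect is small. Over the assumed normal spreads about 1-5% of women are affected, or up to about 13% if all Day 82 visits count. The change scores lose a little precision, without bias if visit timing is unrelated to pain. The weekly plots do read slightly low at Week 12 in both arms, because missing is counted as failure. This is an optional improvement to descriptive outputs, and no sensitivity analysis of the primary endpoint is needed. Confidence is medium, because the size depends on assumed visit dates.

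**What to change.** 1. In SAP 4.3.1.3, for the Week 12 change in weekly average worst pain and in pain-free days only: when an in-window Visit 7 (Days 81-89) leaves fewer than 5 possible diary days in Days 78-84, use the 7 diary days immediately before Visit 7, with the same 5-of-7 rule.
2. Keep the fixed, non-overlapping weeks for the 12-week responder endpoints and the weekly responder plots. Footnote on the plots how many women could not be evaluated at Week 12 because of an early permitted visit.
3. State whether the SAP windows or protocol 9.4.2 govern by-visit diary summaries. List the departure in SAP Section 9 if the redacted text does not already do so.
4. Extend item 1 to the bowel movement diary only if its redacted derivations use the same minimum-entry rule.

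The cost is a few lines of SAP text and code and two footnotes. The downside is that, for these few women, Week 12 in the change-score tables covers Days 74-80 or 75-81 instead of Days 78-84, which the table footnote should say. The overlap with Week 11 does no harm there, because those tables use only Weeks 2, 4, 8 and 12.

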4.3. Data Definitions and Derivations

4.3.1. Efficacy Endpoints

Efficacy Assessments will be collected as outlined in [Table 6](#) below. Refer to protocol section 1.3 (Schedule of Assessments) for the details on the day of visit and timing of measurement.

Table 6: Efficacy Assessments

Assessment	Form	Measurement and Timing
Abdominal Pain Intensity	Daily Evening Pain Diary (eDiary)	Subjects will record daily worst abdominal pain over the past 24-hours with 0- to 10-point NRS (0 = no pain, 10 = worst possible pain) during both Run-in and Double-blind Period
PRO Questionnaires	
 Global Improvement Scale (GIS) 	
 GIS: Day 1, Weeks 2, 4, 8, 12
Additional abdominal pain questions	Daily Evening Pain Diary (eDiary)	
Day 1, Weeks 2, 4, 8, 12
 
 Abdominal pain within 1 hour of eating Abdominal pain associated with a bowel movement

Assessment	Form	Measurement and Timing

There are responders and efficacy endpoints that require further details to clearly define the endpoints without ambiguity. The endpoints and their definitions are described in detail below.

4.3.1.1. API Weekly Responder

To derive API Weekly Responder during various week intervals, the initial two steps should be followed to derive (1) Weekly average worst abdominal pain (WAP) score; (2) Weekly Responder status by week

Step 1:

- Weekly average is defined as the sum of WAP scores on the NRS (0-10) in the 7 days immediately prior to baseline visit (Day 1) or each of post-baseline Weeks (Week 1-Week 12), divided by the number of days with non-missing pain diary entries during the 7 days. Weekly average will be set missing if there are more than 2 missed diary days over the past 7 days.
- API Weekly Responder with $\geq 30\%$ improvement at each week (i.e., Week 1, Week 2, Week 3, ..., Week 12) is defined as a subject who experiences a decrease in the weekly average of WAP score of at least 30% compared with the baseline weekly average. To qualify as a responder for the specific week, a subject must have at least 5 days of non-missing pain diary entries during the week (i.e., ≥ 5 of 7 days). A Subject will be assigned as non-responder for the specific week if the weekly average is missing.

Similarly, the API Weekly Responder will be further derived based on more stringent measures of weekly reduction as below:

- API Weekly Responder with $\geq 40\%$ improvement at each week (i.e., Week 1, Week 2, Week 3, ..., Week 12) is defined as a subject who experiences a decrease in the weekly

average of WAP score of at least 40% compared with the baseline weekly average. To qualify as a responder for the specific week, a subject must have at least of 5 days of non-missing pain diary entries during the week (i.e., ≥ 5 of 7 days).

- API Weekly Responder with $\geq 50\%$ improvement at each week (i.e., Week 1, Week 2, Week 3, ..., Week 12) is defined as a subject who experiences a decrease in the weekly average of WAP score of at least 50% compared with the baseline weekly average. To qualify as a responder for the specific week, a subject must have at least of 5 days of non-missing pain diary entries during the week (i.e., ≥ 5 of 7 days).

Step 2:

Then API Weekly Responder will be derived during different treatment intervals using primary criteria as an example below:

API Weekly responder with $\geq 30\%$ improvement over 12 weeks (i.e., from randomization through to Week 12) - primary efficacy endpoint

- To qualify as an overall API Weekly Responder from randomization through to Week 12 (Weeks 1-12), a subject must satisfy the following criteria:
 - Must meet the API Weekly Response criteria $\geq 30\%$ improvement on $\geq 50\%$ of weeks, i.e., success on 6 or more weeks during the past 12 weeks
 - Must have had ≥ 60 diary days over the past 12 weeks

API Weekly responder from randomization through to Week 2 (Weeks 1-2)

- To qualify as an API Weekly Responder from randomization through to Week 2, a subject must satisfy the following criteria:
 - Must meet the API Weekly Response criteria on more than 50% of weeks, i.e., success on 1 or 2 weeks during past 2 weeks
 - Must have had ≥ 10 diary days over the past 2 weeks

API Weekly Responder from randomization through to Week 4 (Weeks 1-4)

- To qualify as an API Weekly Responder over 4-week interval, a subject must satisfy the following criteria:
 - Must meet the API Weekly Response criteria on more than 50% of weeks, i.e., success on 2 or more weeks during past 4 weeks
 - Must have had ≥ 20 diary days over the past 4 weeks

API Weekly Responder from randomization through to Week 8 (Weeks 1-8)

- To qualify as an API Weekly Responder over 8-week interval, a subject must satisfy the following criteria:
 - Must meet the API Weekly Response criteria on more than 50% of weeks, i.e., success on 4 or more weeks during past 8 weeks
 - Must have had ≥ 40 diary days over the past 8 weeks

The secondary efficacy endpoints of Weekly API Responder with either $\geq 40\%$ or $\geq 50\%$ improvement will be classified using the same rules above.

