The estimated common risk difference, and associated p-value and 2-sided 90% confidence interval will be tabulated. The stratified strata is based on the baseline abdominal pain score which is the average from 7 days immediately prior to the baseline visit. If more than 10% mis-classification of the stratification factors (randomization stratification vs. actual stratification values) happens a sensitivity analysis will be carried out to repeat the primary analysis where the actual stratification will be used in the model (See [Section 6.1.2](#)).

The number and percentage of responders with $\geq 30\%$ improvement over Weeks 1-2, Weeks 1-4, Weeks 1-8 and Weeks 1-12 will be summarized by treatment. The proportion of subjects who meet the Weekly responder criteria at each week will be plotted by treatment.

To assess the impact of missing data, a categorical summary of missing pain and bowel movement diary day entries, summarized by week, will be provided with the categories of none, 1-2, > 2 days, > 3 . The denominator used for the percentages will be the number of subjects who completed diaries for the given week.

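### Does the mismatch between the wording and the week counts in the Weeks 1-2, 1-4 and 1-8 responder rules leave those rules undefined?

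*SAP*

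**What the plan says.** SAP Section 4.3.1.1, Step 2, turns weekly response into response over an interval.

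- **Weeks 1-12 (primary).** The subject must respond in at least half the weeks, spelled out as "success on 6 or more weeks during the past 12 weeks", and must have at least 60 diary days.
- **Weeks 1-2.** "Must meet the API Weekly Response criteria on more than 50% of weeks, i.e., success on 1 or 2 weeks during past 2 weeks", with at least "10 diary days over the past 2 weeks".
- **Weeks 1-4.** "Must meet the API Weekly Response criteria on more than 50% of weeks, i.e., success on 2 or more weeks during past 4 weeks", with at least 20 diary days.
- **Weeks 1-8.** "Must meet the API Weekly Response criteria on more than 50% of weeks, i.e., success on 4 or more weeks during past 8 weeks", with at least 40 diary days.

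Step 2 opens by saying that interval response is "derived during different treatment intervals using primary criteria as an example below". It closes by carrying the rules to the stricter thresholds: the 40% and 50% versions of "improvement will be classified using the same rules above".

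The shorter intervals are planned output. SAP Section 6.1.1 says that responders with "improvement over Weeks 1-2, Weeks 1-4, Weeks 1-8 and Weeks 1-12 will be summarized by treatment". The list of output tables in Section 11.1.1 asks for all intervals, with Weeks 1-12 first, in Table 14.2.1.1 (30%), its per-protocol version 14.2.1.2, and Tables 14.2.1.4 and 14.2.1.6 (40% and 50%). Tables 14.2.1.1, 14.2.1.4 and 14.2.1.6 are marked for topline delivery.

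**The concern.** A strict majority of 2, 4 or 8 weeks is 2, 3 or 5 weeks. The SAP gives 1, 2 and 4. For a subject who responds in exactly half the weeks, the words say non-responder and the count says responder, and both cannot be followed.

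Exactly half is not a rare outcome when an interval holds only two or four weeks. If a production programmer and a validation programmer read the bullet differently, the rates in several tables would differ, some of them topline. A reader of the report who relied on the verbal description would also misunderstand what the rows show. In a study whose stated aim is estimation (SAP Section 1.2.3), the definition behind a reported proportion matters.

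**Working it through.** **1. Minimum number of successful weeks under each reading.** For an interval of n weeks, a strict majority needs floor(n/2) + 1 weeks and half or more needs ceil(n/2).

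| Interval | n | Strict majority | Half or more | SAP count | SAP count / n |
|---|---|---|---|---|---|
| Weeks 1-2 | 2 | 2 | 1 | 1 | 50% |
| Weeks 1-4 | 4 | 3 | 2 | 2 | 50% |
| Weeks 1-8 | 8 | 5 | 4 | 4 | 50% |
| Weeks 1-12 | 12 | 7 | 6 | 6 | 50% |

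The SAP's count equals the half-or-more value in all four rows and the strict-majority value in none. In the Weeks 1-12 row the words also say half or more, so that rule is consistent.

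**2. Which reading the SAP supports.**

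- Each bullet restates the share as an integer count. The Weeks 1-2 bullet names one successful week as sufficient, so it cannot be read as two of two.
- The intervals are introduced as following the primary criteria, and the primary criterion is half or more.
- A responding week already needs at least 5 diary days. Under a two-of-two rule, a responder over Weeks 1-2 would have at least 2 × 5 = 10 diary days, and the separate 10-day condition would do nothing. Under one of two, only 5 days are guaranteed, so the condition has a purpose. This argument covers Weeks 1-2 only: three of four guarantees 3 × 5 = 15 days against 20 required, and five of eight guarantees 5 × 5 = 25 against 40.

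**3. What miscoding would do.** The documents give no single-week response rates or within-subject correlations, so these are assumptions: weekly rate p of 35% to 50%, correlation r between weeks of 0.3 to 0.7, complete diaries, beta-binomial model. For two weeks the formulas are

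- P(both weeks) = p² + r·p(1 − p)
- P(at least one week) = 2p − P(both weeks)

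At p = 0.35 and r = 0.5, P(both) = 0.1225 + 0.5 × 0.2275 = 0.236 and P(at least one) = 0.70 − 0.236 = 0.464. The stated count gives 46.4% and the strict words 23.6%.

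Over the whole range, the Weeks 1-2 results run from 50.9% against 19.1% (p = 0.35, r = 0.3; ratio 0.37) to 57.5% against 42.5% (p = 0.50, r = 0.7; ratio 0.74). The ratios are 0.55 to 0.85 for Weeks 1-4 and 0.71 to 0.92 for Weeks 1-8.

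The difference between arms moves less. Take weekly rates of 51% and 31%, borrowed from the sample-size section, where they are not stated as single-week rates, and r = 0.5:

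| Interval | Difference, stated count | Difference, strict words |
|---|---|---|
| Weeks 1-2 | 21.8 points | 18.2 points |
| Weeks 1-4 | 22.5 points | 20.3 points |
| Weeks 1-8 | 22.8 points | 21.5 points |

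These figures compare the plan with a reading that step 2 rules out. They show what a coding error would cost. They do not show an error in the planned results.

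**4. What a correction would change.** Rewording the three bullets to half or more leaves the counts at 1, 2 and 4. Every subject keeps the same classification at the 30%, 40% and 50% thresholds, so the change in every planned result is zero.

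**The case for a change.** The case for acting is that the contradiction is plain on the page, in a section meant to define the endpoints without ambiguity. It reaches several tables, some of them topline, and carries over to two further thresholds. For Weeks 1-2 the two readings can give rates that differ by a factor of two or more. The correction is a couple of words in three bullets, and settling it before unblinding would prevent any suspicion that the choice followed the data.

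Some of this stands. The words are wrong, and they are ordinary words rather than a symbol lost in conversion. The size of the gap between the readings is also correct under its assumptions.

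The risk of divergent coding does not stand. A programmer implements the integer that each bullet supplies, and that integer agrees with the primary rule. The suspicion of a later choice also fails, because the counts are already fixed in the SAP. A report that restates the counts describes the rows correctly.

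**Conclusion.** No change to the plan follows. The verbal share in three bullets is a clerical slip, the operative counts beside it are explicit, and they match the Weeks 1-12 rule. The effect on planned results is nil, provided that the stated counts are the ones coded; every cue in SAP Section 4.3.1.1 points that way.

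The affected rows are neither primary nor secondary endpoints. The exploratory endpoint list is redacted, so whether they are named there cannot be seen. The primary endpoint and the 40% and 50% secondary endpoints use 6 of 12 weeks and are untouched, as is the power statement. SAP Section 4.1.2 treats all efficacy analyses as descriptive, so no formal decision depends on these rows.
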